# 3. Objectives and hypothesis

#### 3.1. Objectives

To evaluate the improvement in venous reflux following Vitis vinifera seed extract (Enteron®) administration in patients with varicose veins of the lower extremities.

#### 3.2. Hypothesis

We hypothesize that, among patients with vericose veins, the severity of symptoms is likely to

escalate in correlation with the increasing severity of venous reflux. We posit that the medication of Vitis Vinifera seed extract (Enteron®) will contribute to the improvement of venous reflux, subsequently leading to a reduction in symptoms.

#### 3.3. Primary endpoint

Change in venous reflux time [Time Frame: 6, 12 weeks]: We will assess the changes in venous reflux time of target vessel using lower-limb venous Doppler ultrasound examinations.

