symptomatic improvement by lower extremity venous Doppler ultrasonography at 6 and 12 weeks post-treatment follow-up. Patients with Varicose Vein of Lower Extremity Prolonged venous reflux time (superficial vein ≥ 0.5 sec, deep vein ≥ 1 sec) (N=200) Randomization Vitis Vinifera Extract (Entelon®) + Therapeutic lifestyle changes only Therapeutic lifestyle changes (N=100)(N=100)Primary endpoint: Change in venous reflux time from baseline to 6, 12 weeks Secondary endpoint: improvement of venous veflux (superficial vein < 0.5 sec, deep vein < 1 sec) Change from baseline to 6, 12 weeks in vessel diameter, venous reflux volume, clinical status by VCCS, CIVIQ-14 Inclusion 1) Adult males and females aged between 19- and under 80-years-old 2) Patients with the following findings on venous Doppler ultrasound criteria examination: - Superficial veins (such as the great saphenous vein, small saphenous vein, etc.) showing venous reflux for 0.5 seconds or longer - Deep veins (such as the femoral vein, etc.) showing venous reflux for 1 second or longer 3) Patients who have completed the washout period as described below by Visit 2, including the screening period: - Analgesics, steroids, anti-inflammatory drugs, and venoactive medications (such as Entelon®, etc.): at least 4 weeks 4) Patients who voluntarily provide written informed consent to participate in this clinical trial **Exclusion** 1) Peripheral arterial occlusive disease in the lower limbs criteria 2) Asymptomatic lower extremity varicose veins 3) Acute deep vein thrombosis 4) Frequent lower limb pain due to neuropathy 5) Patients who have undergone or are scheduled for varicose vein procedures/surgeries (However, patients who have undergone a procedure or surgery more than 1 year prior to the screening date are eligible to participate.) 6) Patients diagnosed with systemic diseases causing edema or thrombosis, heart failure. endocrine diseases such as (hypothyroidism, Cushing's syndrome, uncontrolled diabetes), allergic reactions to medications, urticaria and angioedema,

malabsorption and protein-calorie malnutrition, obstructive sleep apnea, or thrombophilia, as determined by the investigator

- A. History of malignancy within the past 5 years, but the following cases are eligible for clinical trial participation:
- B. Those who have a history within the past 5 years but maintain a cured state without recurrence or metastasis

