#### Sample size

#### 200 patients

# Sample size calculation

This study is an exploratory study to determine the effectiveness of venous reflux improvement after medication in patients with varicose veins, and there are limited prior studies to draw upon. Therefore, the study design is subject to a number of assumptions. In addition, it is not advisable to apply the same process for calculating the number of patients to meet the mathematical basis for a confirmatory study as for a confirmatory study when controlling for type 1 and type 2 errors.

Nevertheless, a few assumptions can be made to develop a power calculation process that is similar to that of a confirmatory study. According to the literature, the duration of reflux was measured slightly differently at each point, and we would like to calculate the number of

patients based on GSV, prox, which had the largest number of patients (Reference: J Vasc Surg. 2004 Aug;40(2):303-10.). In this study, we would like to conduct an analysis on the difference between the means, but no relevant evidence was found; therefore, we borrowed the median value of the references as the mean. This assumes that the number of n is large enough (174) according to the principle of central limit theorem, such that the gap between the median and the mean is not large. We also calculated the standard deviation using the range and the number of n. By calculating the standard deviation of other parameters together, we found that the standard deviation of the valve-carrying segments can be assumed as approximately 1.8 overall. The results of the drug group are expected to improve by about 10% to 15%, and we decided to conservatively assume an improvement of 12.5% to calculate the number of patients.

Valve-carrying	n	Median (s)	Range (s)
segment			
GSV, prox	174	6.1	0.7-10.0
GSV, dist	84	3.5	0.7-10.0
SSV	91	4.6	0.6-10.0

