## 4. Research protocol and trial design

This study is designed as an investigator-initiated, single-center, open-label, pragmatic, randomized controlled trial. Patients with symptoms of lower extremity discomfort and leg edema and demonstrable venous reflux on lower extremity venous Doppler ultrasound ( $\geq 0.5$  seconds in superficial veins or  $\geq 1$  s in deep veins) will be screened for inclusion in the study. All patients who meet the inclusion criteria will be considered for inclusion.

[figure not shown]
Patients who are eligible for randomization will be randomized 1:1 to the therapeutic lifestyle change (TLC) only arm (control arm) or the medication (Entelon®) plus TLC arm (test arm). The patients will be treated for 12 weeks according to their assigned treatment arms. Patients will be evaluated for improvement in venous reflux in the target vessels and symptomatic improvement using lower-extremity venous Doppler ultrasonography at 6 and 12 weeks post-treatment.

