## 11. Data Analysis & Statistical Considerations

#### 11.1. Sample size calculation

This is an exploratory study to determine the effectiveness of medication in improving venous reflux in patients with varicose veins, and there are limited prior studies to draw upon. Therefore, the study design is based on some assumptions, and it is not advisable to apply the same process to calculate the number of participants that are required to meet the mathematical basis for a confirmatory study when controlling for type 1 and type 2 errors.

Nevertheless, a few assumptions can be made to develop a power-calculation process similar to that of a confirmatory study. According to the literature, the duration of reflux was measured slightly differently at each point, and we calculated the number of participants based on the GSV, prox, which had the largest number of patients (Reference: J Vasc Surg. 2004 Aug;40(2):303-10.). In this study, we examined the difference between the means, but we could not find any evidence; therefore, we used the median value of the references as the mean. This assumes that n is sufficiently large (174), according to the principle of the central limit theorem, so the gap between the median and mean is not large. We also calculated the standard deviation using the range and number of n. By calculating the standard deviations of the other parameters together, we found that the standard deviation of the valve-carrying segments can be assumed to be approximately 1.8 overall. The results of the drug group are expected to improve by approximately 10% to 15%; therefore, we decided to conservatively assume an improvement of 12.5% to calculate the number of participants.

Valve-carrying	n	Median (s)	Range (s)	sd
segment				
GSV, prox	174	6.1	0.7-10.0	1.737
GSV, dist	84	3.5	0.7-10.0	1.921
SSV	91	4.6	0.6-10.0	1.918

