In this case, assuming a normal distribution and based on a Z-test with the same variance in both groups, the following calculation result was obtained under  $\alpha$ =0.025,  $\beta$ =0.2. The calculations were performed using the PASS15. A one-tailed test was performed to determine superiority if the difference between the drug and lifestyle treatment groups was less than zero. Assuming that patients may drop out during the study, the dropout rate was set at 20% to account for dropouts in a typical clinical setting. Therefore, the total number of participants was calculated as 160, with 80 participants in each group. Considering a dropout rate of 20%, we plan to recruit 200 participants, 100 in each group, to conduct the study.

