#### 11.2. Statistical analysis plan

Categorical variables will be expressed as percentages and numbers and will be compared using the Chi-square or Fisher's exact test. Continuous variables will be presented as means, standard deviations, medians, and interquartile ranges and will be compared using an independent two-sample t-test or Wilcoxon rank sum test, while the normality of the underlying variable distribution will be estimated using histograms, skewness, kurtosis, and the Kolmogorov-Smirnov test.

The primary outcome will be presented and compared between the two groups using an independent two-sample t-test. Normality of the empirical distribution of the primary outcome will be evaluated. If this assumption is violated, a nonparametric Wilcoxon rank-sum test will be used. Secondary outcomes will also be summarized and compared between groups using independent two-sample t-tests for continuous outcomes, or chi-square test or Fisher's exact test for categorical outcomes. Considering the factors that may influence the outcome, aside from the randomly assigned intervention, we will conduct an analysis involving the adjustment of the baseline characteristics for primary and secondary outcomes. This careful analytical strategy ensures that our findings are not confounded by pre-existing differences, thereby allowing us to assess the true impact of the intervention more accurately. A planned, exploratory subgroup analysis will be performed to compare the treatment effect in patients with vericose veins with and without Entelon® medication. Unless otherwise specified, all tests will be performed at a significance level of 0.05. All analyses will be performed using SAS 9.4 (SAS Institute Inc., Cary, NC, USA). Statistical support will be provided by [name].

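### The primary endpoint is set at both 6 and 12 weeks and the plan does not say which visit decides, although the sample size covers one comparison

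*Combined protocol and SAP*

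**What the plan says.** The primary endpoint appears three times, each time at two visits. Section 3.3 and the endpoint list in the research summary (section 1) both read "Change in venous reflux time [Time Frame: 6, 12 weeks". The flow chart in the summary reads "Primary endpoint: Change in venous reflux time from baseline to 6, 12 weeks".

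On analysis, section 11.2 says: "The primary outcome will be presented and compared between the two groups using an independent two-sample t-test". A Wilcoxon rank-sum test replaces the t-test if normality fails. On the level, it says: "Unless otherwise specified, all tests will be performed at a significance level of 0.05". It does not state sidedness, name a visit, describe a model over both visits, give a rule for combining them or adjust for two tests.

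Section 11.1 sizes one comparison at alpha 0.025 and beta 0.2, with the direction stated: "A one-tailed test was performed to determine superiority if the difference between the drug and lifestyle treatment groups was less than zero". The summary's PASS output gives 80 per group and power 0.80260. Allowing for 20% dropout, the plan recruits 200.

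Three features bear on the intended reading:
- Section 4 says: "The patients will be treated for 12 weeks according to their assigned treatment arms".
- Sections 7.3, 7.4 and 14 label week 6 as a midterm or interim assessment and week 12 as the end or closing visit.
- All six secondary endpoints in section 3.4 carry the same two-visit time frame.

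Section 11.1 also says: "This is an exploratory study to determine the effectiveness of medication in improving venous reflux in patients with varicose veins".

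**The concern.** The endpoint definition produces two treatment comparisons, and the sample size provides for one. Followed as written, the plan yields two unadjusted primary tests and does not say how their results combine into a conclusion. Three rules are possible: one visit decides, either visit suffices, or both must succeed. They have different false-positive rates and different power, so the properties calculated in section 11.1 belong to the trial only under the first.

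Timing matters too. If the deciding visit is chosen after both results are known, nobody can show that the choice was independent of those results. Section 8.5 provides for a Doppler assessor who is unaware of group assignment. That protects the measurement, but not the later choice of visit.

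**Working it through.** **Inputs from the documents.** Difference 0.8 s (5.3 against 6.1), SD 1.8 s, one-sided alpha 0.025, power 0.80, 1:1 allocation, dropout 20% (section 11.1 and the PASS output in the summary).

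**Inputs assumed.** The documents give no correlation r between the week-6 and week-12 test statistics, so I show 0.3 to 0.95. Section 11.2 does not state sidedness, so I show both readings of its 0.05.

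**1. The plan's own figure.**
- n per arm = 2 × 1.8² × (1.960 + 0.842)² / 0.8² = 79.5, rounded up to 80.
- With 80 per arm, the standard error is 1.8 × √(2/80) = 0.2846 and the noncentrality is 0.8 / 0.2846 = 2.811.
- z-test power = Φ(2.811 − 1.960) = 0.8026, which matches 0.80260.
- Dropout: 80 / (1 − 0.20) = 100 per arm, 200 in total.
- The t-test planned in section 11.2, with 158 degrees of freedom, gives 79.8% on the same inputs.

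The calculation reproduces, and it is for one test.

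**2. If either visit may support superiority.** With no effect at either visit, the false-positive rate is 1 − P(Z1 < c, Z2 < c), where Z1 and Z2 are bivariate normal with correlation r. Here c = 1.960 for one-sided 0.025 (two-sided 0.05) and c = 1.645 for one-sided 0.05.

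| r | Each test at one-sided 0.025 | Each test at one-sided 0.05 |
|---|---|---|
| 0.3 | 4.76% | 9.29% |
| 0.5 | 4.54% | 8.78% |
| 0.7 | 4.17% | 8.04% |
| 0.9 | 3.52% | 6.81% |
| 0.95 | 3.23% | 6.29% |

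Example at r = 0.5, one-sided 0.025: 1 − 0.9546 = 0.0454. For any r below 1 the first column exceeds 2.5%.

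**3. If both visits must succeed, each at one-sided 0.025.**
- False-positive rate with no effect at either visit: P(Z1 > 1.960, Z2 > 1.960) = 0.24% (r = 0.3) to 1.77% (r = 0.95).
- With the 0.8 s effect at one visit and none at the other: 2.4% to 2.5%. A joint success requires rejection at the visit with no effect, so 2.5% is the ceiling.
- Power with 0.8 s at both visits: Φ₂(0.851, 0.851; r), where Φ₂ is the bivariate normal distribution function and 0.851 = 2.811 − 1.960. This gives 67.0% (r = 0.3), 69.1% (0.5), 71.6% (0.7), 75.3% (0.9) and 76.8% (0.95).
- If the week-6 effect were 75% of the week-12 effect, the week-6 term becomes 0.75 × 2.811 − 1.960 = 0.148 and power falls to about 48% (r = 0.3) to 56% (r = 0.95). The documents give no week-6 effect, so 75% only shows the sensitivity.

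**4. If one visit is named.** The false-positive rate is 2.5% in the favourable direction, and the calculation in step 1 applies as it stands.

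**The case against.** The strongest reply is that week 12 is plainly meant. Week 6 is labelled as a midterm or interim look, week 12 as the close, and treatment lasts 12 weeks. The superiority statement concerns a single difference. Because every secondary endpoint carries the same time frame, it may be no more than a measurement schedule. This carries weight as evidence of intent, but none of these features ties the primary test to a visit. If the time frame is only a schedule, the plan has no primary analysis time point at all.

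The second reply is that the study is exploratory. The summary says "it is not advisable to apply the same process for calculating the number of patients to meet the mathematical basis for a confirmatory study". That limits the severity and weakens any demand for formal multiplicity control as such. It does not supply a deciding visit, and the same sections still set up a one-tailed superiority test with a stated alpha and power.

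A reader might infer from step 2 that the trial's false-positive rate is 4.8%, or even 9.3%. The documents do not support that. They contain no either-visit rule and no correlation, and the larger figure also needs the 0.05 in section 11.2 to be applied one-sided, against the one-sided 0.025 used for sizing. These figures are conditional illustrations. What is established is the missing rule.

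**Conclusion.** The point holds as an omission that should be fixed before analysis. The primary endpoint is placed at two visits, the analysis section has no deciding visit, combination rule or adjustment, and the sample size serves one comparison.

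Its size depends on the rule eventually applied:
- **Either visit:** a one-sided false-positive rate of 3.2% to 4.8% at one-sided 0.025 per test, or 6.3% to 9.3% if 0.05 were used one-sided, for assumed r from 0.95 to 0.3.
- **Both visits, each at one-sided 0.025:** at most 2.5%. Power is 67% to 77% only if the 0.8 s effect is equal at both visits, and lower if the week-6 effect is smaller.
- **One named visit:** 2.5%, with the nominal power of section 11.1.

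A reader might also conclude that naming week 12 secures 80.3% power. It leaves the nominal calculation untouched (80.3% by z-test, 79.8% by the planned t-test), but does not verify it. Section 11.1 derives the SD of 1.8 s from published ranges of reflux time, while the endpoint is a change from baseline, and the documents give no SD for the change.

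**What to change.** In section 3.3, and in the flow chart and endpoint list of the summary, name change in venous reflux time from baseline to week 12 as the single primary endpoint, and move change to week 6 to the secondary list. The reason for week 12 is that it is the end of the planned treatment period. Single-comparison sizing alone would fit either visit.

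In section 11.2, state that the primary test is the week-12 comparison at two-sided 0.05, equivalent to one-sided 0.025 in the favourable direction. This matches section 11.1 and settles the unstated sidedness.

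If the sponsor wants a rule that uses both visits, it should be written down before analysis with its own alpha and sample-size calculation.

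The cost is protocol and SAP wording. N=200 and the nominal one-test power calculation do not change. The downside is that success can no longer be claimed on week 6 alone.

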#### 3.4. Secondary endpoint

## 1) Improvement of venous reflux [Time Frame: 6, 12 weeks]

- We will assess the improvement of venous reflux of target vessel (superficial vein < 0.5 seconds, deep vein < 1 seconds)

#### 2) Change in varicose vein size area [Time Frame: 6, 12 weeks]

- We will assess changes in varicose vein diameters of target vessel using lower-limb venous Doppler ultrasound examinations.

#### 3) Change in venous reflux volume [Time Frame: 6, 12 weeks]

- We will assess the changes in venous reflux volume of target vessel using Venous Doppler Reflux VTI × varicose vein size area.

#### 4) Change of extracellular water ratio of target limb [Time Frame: 6, 12 weeks]

- We will assess the changes in extracellular water (ECW) ratio (ECW/total body water) of target limb using body composition analyzer (ACCUNIQ BC720® )

## 5) Improvement in VCSS [Time Frame: 6, 12 weeks]

[figure not shown]
- The Venous Clinical Severity Score (VCSS) assesses the severity of chronic venous diseases. The score ranges from 0 (no symptoms) to 30 (severe venous disease). The scoring system considers various factors, including pain; varicose veins; venous edema; skin pigmentation; inflammation; induration; and active ulcers and their duration, size, and number. A higher VCSS indicates a worse outcome, implying a more severe state of venous disease.

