#### 4.3. Therapeutic lifestyle changes group

Implementing TLCs is a critical component of a comprehensive treatment plan for varicose veins. These non-invasive interventions focus on amending daily habits and behaviors that contribute to the progression of the condition and exacerbation of symptoms. A key aspect of TLCs is the optimization of postural habits. Patients are advised to avoid extended sitting or standing periods, which exert additional pressure on the venous system in the lower extremities and exacerbate venous insufficiency. During rest periods, elevating the legs closer to the heart is recommended because this simple yet effective adjustment promotes venous return and reduces the gravitational burden on the venous valves of the legs. The use of graduated compression stockings during waking hours is another therapeutic lifestyle intervention that is often prescribed for patients with varicose veins. These stockings exert the highest amount of pressure on the ankle, with the pressure gradually decreasing up the leg, thereby mimicking the

physiological pumping function of the calf muscles. This supports the veins in pushing blood back towards the heart, improving overall blood circulation and reducing leg swelling and discomfort associated with varicose veins.

Additional TLCs include maintaining optimal body weight and engaging in regular physical exercise. Being overweight or obese can increase intra-abdominal pressure, which can impose an additional burden on the leg veins. Regular physical activity, specifically exercises that engage the calf muscles, can improve muscle tone, enhance the efficiency of the calf muscle pump, and consequently, improve venous return. Walking or cycling are often recommended because of their effectiveness in promoting lower limb venous return.

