#### 4.4. Medication + TLC group

Patients selected for the combined approach of pharmacotherapy and lifestyle modifications will receive Entelon® 150 mg twice daily for a duration of 12 weeks. This pharmacological intervention should be complemented by the adoption of improved lifestyle habits, including wearing compression stockings.

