#### 7.3. Visit 3 (Midterm Assessment Visit, 6 weeks from randomization visit)

- 1) Lower extremity venous Doppler ultrasound (required)
- 2) Assessment of symptoms: Venous Clinical Severity Score (VCSS), CIVIQ-14
- 3) Performance of blood tests, urinalysis (optional)
- 4) Concomitant medications check (antiplatelet, antithrombotic, antihyperlipidemic).
- 5) Review of lifestyle therapy frequency of stocking wear, pharmacotherapy medication adherence checks
- 6) Monitoring of adverse events

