# 1) VCSS (Venous Clinical Severity Score)

Attribute	Abscent (0)	Mild (1)	Moderate(2)	Severe (3)	Score
Pain	None	Occasional	Daily	Daily with	
				med.	
Varicose veins	None	Few	Multiple	Extensive	
Venous edema	None	Evening only	Afternoon	Morning	
Skin	None	Limited, old	Diffuse, more	Wider,	
pigmentation			recent	recent	
Inflammation	None	Mild cellulitis	Moderate	Severe	
			cellulitis		
Induration	None	Focal <5	<1/3 gaiter	>1/3 gaiter	
		gaiter			
No. of active	None	1	2	>2	
ulcers					
Active ulcer size	None	<2cm	2-6cm	>6cm	
Ulcer duration	None	<3 months	3-12 months	>1 year	
Compression	None	Intermittent	Most days	Fully	
				complaint	
				Total	

Reference: J Vasc Surg. 2011 Dec;54(6 Suppl):2S-9S.

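### The VCSS total counts compression use as worse disease (0 to 3 points) although both arms are advised to wear stockings, and the plan has no rule for separating this item from clinical change

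*Combined protocol and SAP*

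**What the plan says.** Improvement in VCSS at 6 and 12 weeks is the fifth secondary endpoint (Section 1, repeated in Section 3.4). Section 3.4 gives the range, "The score ranges from 0 (no symptoms) to 30 (severe venous disease", and the direction, "A higher VCSS indicates a worse outcome, implying a more severe state of venous disease". Its list of factors runs from pain to "induration; and active ulcers and their duration, size, and number". Compression is not named.

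The form itself is in Section 8.8. Its header is "Attribute Abscent (0) Mild (1) Moderate(2) Severe (3) Score", and the last row before the total is "Compression None Intermittent Most days Fully", so full compliance falls in the severe column and scores 3.

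Stockings are part of treatment in both arms. Section 4.3 (lifestyle changes) says: "The use of graduated compression stockings during waking hours is another therapeutic lifestyle intervention that is often prescribed for patients with varicose veins". Section 4.4 (medication plus lifestyle) says: "This pharmacological intervention should be complemented by the adoption of improved lifestyle habits, including wearing compression stockings".

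Visits 3 and 4 (Sections 7.3 and 7.4) include "Review of lifestyle therapy frequency of stocking wear, pharmacotherapy medication adherence checks". Section 11.2 compares continuous secondary outcomes by two-sample t-test and adds an analysis adjusted for baseline characteristics. It does not mention the compression item or on-study stocking use.

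**The concern.** The endpoint reads a rise in the total as worsening, yet one of the ten items rises when a patient follows the trial's own advice. Two consequences follow.

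- **Within an arm.** Uptake of stockings after screening adds points that offset real improvement elsewhere in the score. The before-after change then understates clinical improvement on the other nine items.
- **Between arms.** Stocking use is a behaviour after randomisation, so randomisation does not guarantee that it stays balanced. Patients know their assignment (Section 4.2), and the blinded assessor is described only for the Doppler examination (Section 8.5). If use of stockings diverges between arms, the divergence on this item goes directly into the VCSS comparison.

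At stake is how a secondary endpoint is read: part of a VCSS difference, or of its absence, could reflect stocking habits and not venous disease.

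**Working it through.** **1. Does the planned total include compression?** The Section 8.8 table has ten items, each scored 0 to 3.
- Ten items: 10 × 3 = 30, which reproduces the stated maximum.
- The nine factors named in Section 3.4 (pain, varicose veins, edema, pigmentation, inflammation, induration, ulcer number, size and duration): 9 × 3 = 27.

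The stated range is reached only with the compression item, so the endpoint as planned includes it.

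**2. Effect on one patient.** VCSS is taken at screening, 6 and 12 weeks (Section 14). With the nine clinical items unchanged, moving from none to intermittent adds 1 point, to most days 2, and to full compliance 3. A patient already wearing stockings fully at screening adds 0.

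**3. Effect on an arm mean.** If a share s of an arm moves from none to full, the mean rises by 3 × s. The documents give no stocking-use figures, so s is assumed:

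| s | Rise in mean VCSS |
|---|---|
| 25% | 0.75 |
| 50% | 1.5 |
| 75% | 2.25 |
| 100% | 3.0 |

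**4. Effect on the between-arm contrast.** If the share moving from none to full differs between arms by d, the item contributes 3 × d. If d = 0, the contribution is 0. Assumed values:
- d = 10 percentage points: 3 × 0.10 = 0.3
- d = 20 percentage points: 3 × 0.20 = 0.6
- d = 30 percentage points: 3 × 0.30 = 0.9

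Lower use in the drug arm makes this contribution look like drug benefit. Higher use there hides a benefit or looks like harm.

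**5. What such a shift could do to the test.** The documents give no SD for VCSS change, so SD = 2, 3 and 4 are assumptions. Take 80 per arm (the plan's evaluable number), two-sided 0.05, a normal approximation, no true clinical difference, and a net arm difference b in the score that comes only from compression. Then SE = SD × √(2/80), and the chance of a significant result is Φ(b/SE − 1.96) + Φ(−b/SE − 1.96).

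| b | SD 2 | SD 3 | SD 4 |
|---|---|---|---|
| 0 | 5% | 5% | 5% |
| 0.25 | 12.4% | 8.2% | 6.8% |
| 0.5 | 35.3% | 18.4% | 12.4% |
| 1.0 | 88.5% | 55.9% | 35.3% |

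For example, with b = 0.5 and SD = 3: SE = 3 × 0.158 = 0.474, b/SE = 1.05, and the total is 18.4%. A b of 0.5 corresponds to d = 0.5/3, about 17 percentage points. These are gross figures: they assume that stockings change no other item.

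**6. After removing the item.** The range becomes 0 to 27, and the compression item itself contributes 0 in steps 2 to 5.

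**The case against.** The strongest reply is that the plan uses a cited ten-item instrument unmodified, which is defensible. The documents offer no support for a nine-item total as a measure in its own right. This stands, and it is why the full total should stay reported.

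Other parts of the case against also stand:
- The same stocking advice goes to both arms, and nothing in the documents points to an adherence gap. The gaps in the working are illustrations.
- Section 4.3 credits stockings with reducing swelling and discomfort, and edema and pain are VCSS items. Adherence could lower those items while raising this one, so the net bias could be smaller than shown or have the opposite sign.
- Washout covers drugs only and Section 9 describes stockings as usual care. Some patients may already wear them at screening and add nothing to the change.
- Stocking frequency is reviewed at Visits 3 and 4, so an imbalance could be seen, and CIVIQ-14 has no compression item. However, Section 11.2 gives the review no role in the VCSS analysis.

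A reader might also see the nine named factors against a maximum of 30 as a contradiction. The documents do not support that: the list is introduced as open-ended, and the table supplies the tenth item. The text is merely silent on an item that matters for interpretation.

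**Conclusion.** The concern holds in a limited form. An element of the treatment advised to both arms is scored as worse disease inside a secondary endpoint, and the analysis plan does not separate it. The item can add at most 3 of 30 points per patient, and only where use rises after screening. Its contribution to the arm contrast is 0.3, 0.6 or 0.9 points for assumed gaps of 10, 20 or 30 percentage points in full versus no use. The net effect on the total is uncertain in size and sign.

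Two stronger readings are tempting but unsupported. One is that stocking use cancels VCSS improvement: the offset is capped at 3 points, depends on baseline use that the documents do not give, and drops out of the between-arm difference when the rise is equal. The other is that any adherence difference would look like a drug effect: on this item only lower use in the drug arm mimics benefit, while higher use works against the drug.

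VCSS is one of six secondary endpoints in a study that calls itself exploratory. The primary endpoint and the sample size are not affected. The change should be made before analysis, so that the choice of score does not depend on the results.

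**What to change.** - In Sections 3.4 and 11.2, prespecify an analysis of change in the sum of the nine clinical items (0 to 27) alongside the 0 to 30 total, and state that VCSS improvement will be interpreted from the nine-item score.
- Report the compression item by arm at baseline (the screening assessment), 6 and 12 weeks as a measure of adherence, next to the stocking-wear review from Visits 3 and 4.
- Name the compression item in the endpoint text of Sections 1 and 3.4, with its scoring direction.

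The cost is wording only. The form has a score for each item, so no new data, visits or patients are needed. The small downside is that a nine-item score is less comparable with published 30-point totals, which is why the full total stays reported. Removing the item does not remove any real effect of stockings on edema or pain. The compression table by arm lets a reader judge whether that could matter.
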